4. REGISTRATION PROCEDURES

4.1 General Guidelines for DF/HCC and DF/PCC Institutions

Institutions will register eligible participants with the DF/HCC Office of Data Quality (ODQ) central registration system. Registrations must occur prior to the initiation of protocol therapy. Any participant not registered to the protocol before protocol therapy begins will be considered ineligible and registration will be denied.

An investigator will confirm eligibility criteria and a member of the study team will complete the ODQ protocol-specific eligibility checklist.

Following registration, participants may begin protocol therapy. Issues that would cause treatment delays should be discussed with the Overall Principal Investigator (PI). If a participant does not receive protocol therapy following registration, the participant's registration on the study must be canceled. Notify the ODQ Registrar of registration cancellations as soon as possible.

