4.3 General Guidelines for Other Participating Institutions

Eligible participants will be entered on study centrally at the DFCI by staff of the coordinating center. Following registration, participants should begin protocol therapy within 5 days.* Issues that would cause treatment delays should be discussed with the Overall PI. If a participant does not receive protocol therapy following registration, the participant's registration on the study must be canceled. The staff at the coordinating center should be notified of cancellations as soon as possible.

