5.2 Screening Criteria

All subjects or their legally acceptable representative and the person who conducted the informed consent discussion must personally sign and date the consent form before any study-specific screening procedures are performed. Procedures that have been performed before consent was obtained as part of routine care are not considered study-specific procedures.

Medical history information to be collected during screening must date back to the original diagnosis of cancer. If a subject is referred to the study center, a copy of all applicable reports and histological or cytological evidence, confirming the diagnosis must be provided to the study center before enrollment. Copies of recent (i.e., within the past 6 months) radiographic images confirming disease progression by modified RECIST should be provided to the study center.

All subjects who have signed the IRB approved consent form must be registered as a screened subject. At the time of registration, the subject will receive a unique 2 digit subject identification number. This number will be used to identify the subject throughout the study and must be used on all study documentation related to that subject. The subject identification number must remain constant throughout the entire study.

All screening tests and procedures must be performed and the results available within a maximum of 14 days before study day 1 unless otherwise noted.

Subjects who do not meet eligibility criteria within the 14 day screening period will not be eligible for enrollment. However, subjects may be re-screened up to 2 additional times at the discretion of the investigator. The subject must be re-consented if more than 28 days have elapsed since the date of last informed consent.

The following screening assessments must be performed:

- Review of inclusion and exclusion criteria
- Medical history review, documentation of diagnosis and previous treatment.
- Physical examination, ECOG performance status, blood pressure, respiratory rate, resting pulse, temperature, height and weight.
- CT scans (contrast-enhanced) or MRI scan (contrast-enhanced) of areas of known disease and that are of acceptable quality as baseline study within 30 days prior to study day 1.

Laboratory assessment consisting of

- Hematology
- Chemistry
- Urinalysis
- beta HCG pregnancy test for women of child-bearing potential

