5.3 Pretreatment Criteria

The first dose of Everolimus may be administered on the same day as enrollment but no more than 10 business days after enrollment. The treatment period begins on the first day of treatment with Everolimus.

If a subject is unable to come into the clinic for a required study visit or if unforeseen events occur, the visit procedures may be performed within a one week time frame.

The following assessments will be performed at each clinic visit according to table 3.4 throughout the treatment period:

- Physical examination,
- ECOG performance status,
- Blood pressure, respiratory rate, resting pulse, temperature, and weight.
- Laboratory evaluations: If patients have met trial eligibility within the previous 72 hours, no specific criteria will need required in order to initiate the protocol unless, in the investigator's opinion, significant medical issues arise which would contraindicate starting the study medications. If patients have completed entry criteria >72 hours prior to cycle 1 day 1, laboratory values on cycle 1 day 1 should be repeated to confirm all eligibility criteria are met.
- CT scans (contrast-enhanced) or MRI scan (contrast-enhanced) or PET-CT scan of areas of known disease every 8 weeks with a 5 business-day time window in case unforeseen events occur. Evaluation according to RECIST criteria compared to previous scan.
- beta HCG pregnancy test for women of child-bearing potential

Documentation of all adverse events will occur at each clinic visit and at any other time point when necessary. There are no specific criteria for the initiation of a given cycle except for the ones indicated in the dose modification tables 6-2, 6-3 & 6-4. Study subjects may commence with treatment if, in the opinion of the investigator and based on the guidance of Section 6, it is safe for the participant to do so.

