9. STUDY CALENDAR

Baseline evaluations are to be conducted within 1-week prior to start of protocol therapy. Scans must be done ≤ 4 weeks prior to the start of therapy. In the event that the participant's condition is deteriorating, laboratory evaluations should be repeated within 48 hours prior to initiation of the next cycle of therapy.

All assessments must be performed prior to administration of any study medication. All study assessments and medications should be administered within **one week** of the protocol-specified date, unless otherwise noted.

Action	Study entry (within 14 days of day 1 unless otherwise noted))	Day1	At clinic visit every 4 weeks* (This may be extended to every 8 weeks after cycle 2 upon investigator's discretion)	Every 8 weeks for max. 24 months*	End of Study
Informed consent	X (within 28 days of day1)				
Medical history and height	X				
Inclusion/exclusion criteria	X				
Vital Signs	X	X	X		X
ECOG Performance status	X	X	X		X
Physical examination and weight	X	X	X		X
AE's and con- medications/treatments	X	X	X		X
Pregnancy test (female subjects <50)	X (in clinic)	X	X (in clinic)	X**	
Hematology and blood chemistry	X	X***	X		X
Urinalysis	X	X (only if abnormal at baseline or clinically indicated)			
CT/MRI chest, abdomen, and other disease sites, as appropriate	X (within 30 days of day 1)			Repeat scans of areas of known disease or of new areas based on clinical judgment	
Everolimus	Administered daily continuously until removal from study				
Cf-DNA blood		X			
Archived tumor sample	Sample must have been acquired no longer than 2 years prior to enrollment in the study				
Tumor biopsy	Participants who achieved either a partial response or stable disease \geq 4 months must agree to a tumor biopsy upon disease progression, assuming it is judged safe and feasible by treating physician				

- +/- one week depending on appointment availability due to holidays or unforeseen events
- **When women of child-bearing age are being seen every two months, it is recommended that they perform home pregnancy testing at 1 month between visits. They should also have an office pregnancy test at every visit. Patients will be contacted by a member of the study team via phone to track the pregnancy tests performed at home.
- ***Hematology and blood chemistry studies need to be assessed on C1D1 only if screening was performed >72 hours prior. In this case laboratory values on cycle 1 day 1 must meet eligibility criteria.

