10.1.5 Duration of Response

Duration of overall response: The duration of overall response is measured from the time measurement criteria are met for CR or PR (whichever is first recorded) until the first date that recurrence or PD is objectively documented, taking as reference for PD the smallest measurements recorded since the treatment started.

Duration of overall complete response: The duration of overall CR is measured from the time measurement criteria are first met for CR until the first date that recurrent disease is objectively documented.

Duration of stable disease: Stable disease is measured from the start of the treatment until the criteria for progression are met, taking as reference the smallest measurements recorded since the treatment started.

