14.1 Study Design/Endpoints

The primary objective of this trial is objective response rate according to RECIST 1.1 criteria.

Secondary objectives include duration of response, progression-free and overall survival. Duration of response is defined as the time from RECIST-confirmed response (CR+PR) to documented disease progression. Progression-free survival is defined as the time from study registration to documented disease progression per RECIST 1.1 or death from any cause, whichever occurs first. Patients not experiencing a PFS event will be censored at the date of their last disease assessment. Overall survival is defined as time from registration to death from any cause, censoring patients thought to be alive at the time of final analysis at the last date of follow up. We will also estimate toxicity via CTCAE version 4.0, and the association of IHC and whole exome sequencing results with patient outcomes and other genetic events.

We will estimate event-time distributions using the Kaplan-Meier method, using Greenwood's formula to estimate the variance and provide 90% confidence intervals for the medians, 6-month, and 1-year estimates. Categorical outcomes, such as toxicity and response, will be estimated and their corresponding 90% exact binomial confidence intervals will be provided.

For the cohort of patients with TSC1 and TSC2 mutations, we will conduct this study using a Simon's two-stage design. In the first stage we will enroll 21 patients and if a total of at least 4 responses (CR + PR) are observed among them, accrual to the second stage will open. If 3 or fewer responses are observed among the first 21 patients, the study will terminate. In the second stage, an additional 29 patients will be enrolled for a total study accrual of 50 patients. After accrual to the second stage is completed, we will declare study success if at least 8 responses are observed among the 50 registered patients. This design has a probability of stopping early after the first stage of accrual of 85% if the drug is ineffective; the overall power of the study to detect the targeted response rate of 30% (compared to a null of 10%) is 91% while controlling the type I error at a one-sided level of 0.07.

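### PFS and OS can be modestly overstated: both clocks start at registration, but a patient who is registered and never dosed has the registration cancelled

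*Combined protocol and SAP*

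**What the plan says.** **Origin.** Section 14.1: "Progression-free survival is defined as the time from study registration to documented disease progression per RECIST 1.1 or death from any cause"; and "Overall survival is defined as time from registration to death from any cause". Section 10.1.6 gives the same origin for PFS.

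**Never-dosed patients.** Section 4.1 states that, for a participant who receives no protocol therapy, the "registration on the study must be canceled". Section 4.3 and Section 3.7.2 of the Data and Safety Monitoring Plan (Appendix C) repeat the rule for external sites.

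**Permitted delay.** Section 5.3 allows the first dose on the day of enrollment, but "no more than 10 business days after enrollment". For external sites, Section 4.3 says "participants should begin protocol therapy within 5 days". Where screening laboratory tests are more than 72 hours old on day 1, Section 9 adds: "In this case laboratory values on cycle 1 day 1 must meet eligibility criteria".

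**Other origins.** Best overall response (10.1.4.3) runs from the start of treatment. So does stable disease in 10.1.5: "Stable disease is measured from the start of the treatment until the criteria for progression are met".

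**Analysis.** Section 14.1 plans Kaplan-Meier medians and 6-month and 1-year estimates with 90% confidence intervals. It gives no null value, test or comparator for PFS or OS. Section 10.1.1 defines who is evaluable for toxicity and for response. Nothing defines who is analysed for PFS and OS.

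**The concern.** A registration origin is sound when everyone registered is analysed from that date. Here a second rule removes patients according to what happens after the origin: to stay registered, a patient must live long enough, and remain fit enough, to take a first dose. Patients who die in the interval disappear, while those who remain are credited with it as event-free time.

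For OS the interval is immortal by construction. For PFS it is nearly so: a patient could progress and still be dosed, but no scan is scheduled between baseline and the 8-week assessment, so progression is unlikely to be documented in the window.

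The trial has one arm, so no control group carries the same bias and cancels it. The confidence interval shows sampling error but not a shift in one direction. The estimates could also depend on how quickly a site starts treatment.

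**Working it through.** The plan states no expected PFS or OS, so there is no figure to reproduce. The check asks how large the shift can be.

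**Inputs from the documents**
- Delay *d* from registration to first dose: 0 days (same-day dosing, 5.3); 5 days (4.3); 10 business days, which is 14 calendar days if no holidays intervene (5.3, taking enrollment as registration).
- Sample size: 30 (14.3) or 50 (14.1, TSC1/TSC2 cohort).

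**Assumptions**
- Exponential event times with median *m*. The working value for PFS is 4 months, with 2 to 12 months shown as a range.
- Every patient has the same delay *d*, and every patient with an event before *d* is excluded.
- One month is 30.4375 days, so 5 days = 0.164 months and 14 days = 0.460 months.

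**Model.** For all registered patients, S(t) = 2^(−t/m). For those who must reach first dose event-free, the curve from registration is S(t)/S(d) = 2^(−(t−d)/m). The median therefore rises from *m* to *m* + *d*, and the rate at time *t* becomes S(t−d). Counting from first dose removes the same *d*.

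**Six-month PFS with m = 4 months**
- d = 0: 2^(−6/4) = 35.4%
- d = 5 days: 2^(−(6−0.164)/4) = 36.4%
- d = 14 days: 2^(−(6−0.460)/4) = 38.3%

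The median rises by 0.164/4 = 4.1% with a 5-day delay and by 0.460/4 = 11.5% with a 14-day delay. The share of registered patients lost before first dose would be 1 − 2^(−d/m): 2.8% and 7.7%.

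**Range over assumed medians**

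| Median (months) | Median shift, 5 d | Median shift, 14 d | 6-month rate: 0 → 5 d → 14 d |
|---|---|---|---|
| 2 | 8.2% | 23.0% | 12.5 → 13.2 → 14.7% |
| 3 | 5.5% | 15.3% | 25.0 → 26.0 → 27.8% |
| 4 | 4.1% | 11.5% | 35.4 → 36.4 → 38.3% |
| 6 | 2.7% | 7.7% | 50.0 → 51.0 → 52.7% |
| 12 | 1.4% | 3.8% | 70.7 → 71.4 → 72.6% |

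For OS with an assumed 12-month median, the 1-year rate goes from 50.0% to 50.5% (5 days) or 51.3% (14 days).

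**Against sampling error.** The 90% half-width of a 35.4% estimate without censoring is 1.645 × √(0.354 × 0.646 / n): 14.4 points at n = 30 and 11.1 points at n = 50. The largest shift at that median is 38.3 − 35.4 = 2.9 points.

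**The case against.** **Exclusion is inferred.** No section says that cancelled registrations leave the PFS/OS analysis, and the success rule in 14.1 counts responses among registered patients. This stands: the overstatement is conditional. Exclusion is nevertheless the natural meaning of cancelling a registration.

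**The 14-day figure is a ceiling.** It needs every patient to start at the limit, and same-day dosing gives no bias. With no scan before dosing, excluded PFS events would mostly be deaths, in patients who had just met the eligibility criteria. This also stands.

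**The cap has a caveat on the other side.** It assumes a constant hazard. The repeat laboratory check on day 1 can also remove patients who are deteriorating. If those have the worst prognosis, the bias could exceed the delay. The documents do not allow this to be sized.

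**Stronger readings that the documents do not support**
- A reader might infer that a patient progressing at the first 8-week scan is wrongly credited with 56 + 14 = 70 days. That patient did progress 70 days after registration. The difference lies between two definitions; bias comes only from patients who are left out.
- A reader might take the consent-stage step in 5.2, where subjects "must be registered as a screened subject", as the PFS/OS origin. Sections 4.1 and 4.2 and Section 3.7.1 of the monitoring plan reserve registration on the study for patients whose eligibility is confirmed. The 5.2 step is a screening record, and only its wording needs separating.
- A reader might see 5 days against 10 business days as proof of bias. A tighter target for external sites can sit inside a general maximum, and one counts from registration, the other from enrollment.
- Different origins for different endpoints are not in themselves an error. The two PFS definitions agree.

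**Conclusion.** The point holds in conditional form. If cancelled registrations leave the analysis, two written rules together push PFS and OS upward. The effect is zero with same-day dosing. Under a constant hazard it is at most the delay to first dose: about 5 days on the external-site target and about 14 calendar days at the 5.3 limit. At an assumed 4-month median that is 1.0 point on 6-month PFS (36.4 − 35.4), and 2.9 points as a ceiling. It would matter in relative terms only if medians were very short and most patients started near the limit.

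A reader might infer that both endpoints are certainly overstated, or that the trial's conclusion is at risk. Neither follows. The documents give no delay distribution, no cancellation count and no expected survival. PFS and OS are secondary and descriptive, and the two-stage decision rests on response counts, which use no time origin. The case for acting is that the shift runs in one direction, the confidence interval does not show it, and it is cheap to remove.

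**What to change.** In 10.1.6 and 14.1, define PFS and OS from the date of the first dose of everolimus, in all patients who receive at least one dose. This is the starting point already used in 10.1.4.3 and 10.1.5. Report the number of cancelled registrations with reasons, so that selection before dosing is visible; moving the clock does not bring those patients back.

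Alternatively, keep the registration origin and state that cancelled registrations stay in the PFS and OS analysis. That would require follow-up of patients never dosed, whereas 5.7 describes follow-up only after removal from treatment.

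As minor wording, reconcile the start-of-therapy intervals in 4.3 and 5.3, say whether enrollment in 5.3 means registration, and use a different term in 5.2 for logging screened subjects.

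The first option costs a few lines of text and no new data, since dosing is already recorded (5.1 and the Treatment Form in 12.1.2). Its downside is slightly shorter PFS and OS.

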3. PARTICIPANT SELECTION

This study will enroll 30 patients with inactivating mutations in TSC1 or TSC2, or activating mTOR mutations.

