14.3 Sample Size/Accrual Rate

We have a planned sample size of 30 patients, with either inactivating TSC1 or TSC2 mutations, or activating MTOR mutations, so it is estimated that this protocol will complete accrual in 48 months, making for an overall accrual rate of approximately 1.25 patients per month. We will be identifying patients for this study from the Oncopanel cancer genotyping at DFCI/BWH, the Impact cancer genotyping panel at MSKCC, and CLIA certified genotyping laboratories both at other DF/HCC institutions and external sites.

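### Minor, reporting only: the 90% exact interval planned for response ignores the TSC1/TSC2 cohort's stop at 21 patients, so 90% coverage is not guaranteed at every true response rate

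*Combined protocol and SAP*

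**What the plan says.** Section 14.1 names one interval method for categorical outcomes, response included: "Categorical outcomes, such as toxicity and response, will be estimated and their corresponding 90% exact binomial confidence intervals will be provided". Later in the same section the TSC1/TSC2 cohort is given a two-stage design: "For the cohort of patients with TSC1 and TSC2 mutations, we will conduct this study using a Simon's two-stage design". The interim rule is "If 3 or fewer responses are observed among the first 21 patients, the study will terminate". If the trial continues, "In the second stage, an additional 29 patients will be enrolled for a total study accrual of 50 patients", and the final rule is "we will declare study success if at least 8 responses are observed among the 50 registered patients".

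No section adjusts the response interval for the interim stop. The only other interval statement for response, later in section 14, concerns the 10-patient mTOR cohort, which has no interim look.

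The total is stated differently elsewhere. Section 3 says "This study will enroll 30 patients with inactivating mutations in TSC1 or TSC2, or activating mTOR mutations", and section 14.3 says "We have a planned sample size of 30 patients".

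**The concern.** Objective response is the primary endpoint. An exact binomial interval is normally chosen because, at a fixed sample size, it covers the true rate at least as often as its label says, whatever that rate is. Here the data decide whether the denominator is 21 or 50. Low stage 1 counts are frozen at 21 patients, where further accrual might have raised the observed rate. That puts extra probability on results whose upper limit lies below the true rate. At stake is the accuracy of the published interval. No decision in the plan uses it.

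**Working it through.** **Inputs (section 14.1).** Stage 1 has n1 = 21 and stops at 3 or fewer. Stage 2 adds 29, for a total of 50. Success is at least 8 of 50. The null rate is 10% and the target 30%. The interval is 90% exact binomial, taken as Clopper-Pearson with 5% per tail, using denominator 21 after a stop and 50 otherwise.

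**Formulas.** Write b(x; n, p) for the binomial probability.
- Stopped with x of 21 (x ≤ 3): probability b(x; 21, p).
- Continued, ending with s of 50: sum over x1 ≥ 4 of b(x1; 21, p) × b(s − x1; 29, p).
- Ordinary limits for x of n: lower is the 5% quantile of Beta(x, n − x + 1); upper is the 95% quantile of Beta(x + 1, n − x).
- Coverage at p: the total two-stage probability of results whose interval contains p.

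**The plan's own figures.** Early stopping at 10% is 0.848 (stated 85%), power at 30% is 0.9125 (stated 91%), and type I error is 0.0662 (stated 0.07). All agree, so the enumerated design is the planned one.

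**Fixed-sample benchmark.** Minimum coverage of the ordinary interval is 91.3% at n = 21 and 90.04% at n = 50 (true rates 2% to 90%, step 0.01 point).

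**Coverage under the stopping rule.**

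| True rate | Coverage of ordinary interval |
|---|---|
| 10% | 98.2% |
| 20% | 95.7% |
| 25% | 94.1% |
| 30% | 90.6% |
| 33.78% | 87.4% (minimum) |

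Coverage is below 90% only on 28.13-28.31% (lowest 89.9%) and 32.93-34.17%, about 1.4 points of true rate in all. Mean coverage in the second band is 89.4%. It is below 89% on only about 0.07 points of true rate, near 33.8%.

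**Why the minimum falls there.** The upper limit is 32.92% for 3/21 and just under 33.78% for 11/50. At a true 33.78%, therefore, every stage 1 stop (probability 0.0423) and every result from 4 to 11 of 50 (0.0347) has an upper limit that is too low. Together these give 0.0423 + 0.0347 = 0.0770, against a nominal 0.05. The lower limit is too high with probability 0.0490. Coverage is 1 − 0.0770 − 0.0490 = 0.8740. Over all true rates the lower-limit error never exceeds 5%.

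**Stage-wise interval.** Order the results 0/21 to 3/21, then 4/50 to 50/50. The lower limit solves P(this result or higher) = 0.05; the upper solves P(this result or lower) = 0.05. Minimum coverage is 90.0%, and it is 90.3% at 33.78%.

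| Result | Ordinary | Stage-wise |
|---|---|---|
| 3/21 | 4.0-32.9% | 4.0-32.9% |
| 4/50 | 2.8-17.4% | 6.8-32.9% |
| 8/50 | 8.2-27.0% | 9.4-33.1% |
| 9/50 | 9.7-29.3% | 10.6-33.6% |
| 12/50 | 14.5-36.0% | 14.7-37.0% |
| 16/50 | 21.2-44.5% | 21.3-44.6% |

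The upper limits differ by more than 4 points only at 4 to 9 of 50. Such a result has probability 17.3% at a true 20%, 7.4% at 25% and 2.0% at 30%.

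**Dependence on the total.** The plan does not split its 30 patients by cohort, so the splits here are assumptions. With 30 TSC1/TSC2 patients and the same stop at 21, minimum coverage is 0.8955, a shortfall of under half a point. If the 30 includes the 10 mTOR patients, 30 − 10 = 20 remain, the 21-patient look is never reached, and the ordinary interval keeps its guarantee (minimum 0.9005 at n = 20).

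**The case against.** The strongest objection is that this hardly matters. The 87.4% is a spike: across the main band the average shortfall is 0.6 points, and coverage at the plan's two reference rates is above 90%. Success is decided by a count. The lower limit, which bears on any claim against 10%, is sound. Section 14.1 names a computation and does not itself promise coverage under the two-stage design. All of this stands, and it makes the point minor.

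The objection to the remedy also has force. The stage-wise upper limit is nearly flat, 32.9% to 33.6% for every count from 4 to 9 of 50. Even 4/50, with no responses among 29 second-stage patients, would not exclude 30%. Among trials that continue at a true 10%, the stage-wise interval covers 75.5% against 88.1% for the ordinary one. Its 90.0% minimum also assumes exactly 21 then 29 patients in the denominator. Section 10.1.1 defines a narrower evaluable group than the registered patients of section 14.1, and section 14.2 allows a discretionary halt by cancer site that the calculation does not model. These are reasons to report the stage-wise interval beside the ordinary one, not in its place.

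A reader might infer that the ordinary interval is wrong when it excludes the 30% target at 8 or 9 of 50, a declared success. The figures do not support that: its upper limit falls below a true 30% in 4.7% of trials, within the nominal 5%.

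**Conclusion.** The point holds as a minor reporting matter. The ordinary exact interval planned for response does not guarantee 90% coverage under the TSC1/TSC2 stopping rule. The loss is at most 2.6 points, typically under 1 point, confined to about 1.4 points of true rate, and always in the upper limit.

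A reader might go further and infer that the interval is generally too narrow, or that the go/no-go rule is compromised. Neither follows: coverage averages 93.1% over true rates of 10% to 40%, and the stated stopping probability, power and type I error all reproduce.

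The conclusion assumes Clopper-Pearson limits, denominators of 21 or 50, and that 21 + 29 is the design actually run. It does not extend to the mTOR cohort. The conflict over the total is a separate and more basic defect, and the size of this point depends on how it is settled.

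**What to change.** 1. Reconcile the 30-patient total in sections 3 and 14.3 with the 21 + 29 TSC1/TSC2 patients and 10 mTOR patients of section 14.
2. If an interim stop remains, state in section 14.1 that for the TSC1/TSC2 cohort a 90% interval from the two-stage sampling distribution, with stage-wise ordering and the final stage sizes, will be reported with the ordinary exact interval. Add that the ordinary interval is not adjusted for the interim stop, that both are descriptive, and that success is decided by the response count. At 8/50 both intervals include 10%, so this last statement avoids an apparent contradiction.
3. Keep the ordinary exact interval for the mTOR cohort and for toxicity.

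The cost is a few sentences and a few lines of code, with no change to sample size, stopping rule or the 8-of-50 criterion. The added interval is slightly wider on average (22.8 to 24.1 points at a true 20%, 23.2 to 23.5 at 30%). Its flat upper limit at 4 to 9 of 50 and its lower coverage among continuing trials at a true 10% should be acknowledged when it is reported.

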For the cohort of 10 patients harboring mTOR mutations, we are somewhat limited in the inferences that can be made, however we would consider observing at least 2 responses in this cohort worthy of additional study. The maximum half-width of the 90% exact binomial confidence interval will be 23.5%.

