14.2 Consideration of gene and mutation specific response rates

It is possible that certain combinations of mutation - primary cancer site will not respond to Everolimus therapy. Though the distribution of histologic subtypes among patients to be enrolled is unknown at this time, it is of interest to conduct exploratory analyses within these subgroups (for example, among patients with bladder cancer, PEComas, squamous cell lung cancer, etc.) Among a subgroup of 10 patients of any particular histology, there is 0.98 probability of observing at least 1 response among them, assuming an underlying response rate of 30%. Therefore, if 10 patients with TSC1/TSC2 mutations and a single cancer site are enrolled and no responses are observed among them, consideration may be given to halting enrollment of patients with cancers arising in that specific site. Since this lack of response may vary according to the primary site of cancer, in that instance we will continue to enroll patients TSC1/TSC2 mutations and different primary cancer sites.

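### The maximum 90% confidence-interval half-width for the 10-patient MTOR cohort is 27.8%, not 23.5%, and the 0.98 behind the 10-patient tumour-site rule should be 0.97

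*Combined protocol and SAP*

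**What the plan says.** Section 14.1 commits the trial to one interval method for response: "Categorical outcomes, such as toxicity and response, will be estimated and their corresponding 90% exact binomial confidence intervals will be provided". It then describes a separate MTOR group ("For the cohort of 10 patients harboring mTOR mutations"), concedes that inference there is limited, and sets a signal threshold: "we would consider observing at least 2 responses in this cohort worthy of additional study". Its statement of precision for the group is "The maximum half-width of the 90% exact binomial confidence interval will be 23.5" percent.

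Section 14.2 deals with exploratory analyses by tumour site. Taking the true response rate to be 30%, it says "Among a subgroup of 10 patients of any particular histology, there is 0.98 probability of observing at least 1 response among them". From this it concludes that, if 10 TSC1/TSC2 patients with one primary site yield no responses, "consideration may be given to halting enrollment of patients with cancers arising in that specific site".

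**The concern.** A maximum half-width tells the reader how imprecise the estimate can be whatever the result. For an exact binomial interval the half-width is greatest when about half the patients respond, so a maximum for 10 patients should be found at 5 responses. The printed figure looks too small for that.

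The sentence matters because 14.1 gives no type I error or power for the MTOR cohort. The half-width is its only stated precision. If it is too small, the plan promises precision that the cohort cannot deliver over the middle of its range of outcomes.

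The 0.98 in 14.2 is the stated reason for considering closure of a tumour site after 0 of 10. If it is too high, the chance of seeing no responses in a site that does respond at the targeted rate is understated.

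**Working it through.** **Inputs.** From 14.1: n = 10 MTOR patients; 90% exact binomial interval, read as two-sided Clopper-Pearson with 5% in each tail; stated maximum half-width 23.5%. From 14.2: n = 10 patients per site; response rate 30%; stated probability 0.98.

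**Half-width.** For x responses in n patients:

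- lower limit = 5th percentile of Beta(x, n − x + 1), or 0 if x = 0
- upper limit = 95th percentile of Beta(x + 1, n − x), or 1 if x = n
- half-width = (upper − lower) / 2

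*Finding the plan's figure.* At x = 2 the limits are 0.0368 and 0.5069, so the half-width is (0.5069 − 0.0368) / 2 = 0.2351, or 23.5%. The printed number is therefore the half-width at 2 of 10, which is the cohort's own signal threshold.

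*All possible results with n = 10:*

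| Responses | Half-width |
|---|---|
| 0 or 10 | 12.9% |
| 1 or 9 | 19.5% |
| 2 or 8 | 23.5% |
| 3 or 7 | 26.0% |
| 4 or 6 | 27.3% |
| 5 | 27.8% |

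At x = 5 the limits are 0.2224 and 0.7776, giving (0.7776 − 0.2224) / 2 = 0.2776. The maximum is 27.8%. The shortfall is 27.8 − 23.5 = 4.3 points of half-width; the full widths are 55.5% and 47.0%.

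*Could another method give 23.5% as a maximum?* None of those tried does so at n = 10:

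| Method | Maximum half-width |
|---|---|
| 80% exact | 23.3% |
| 95% exact | 31.3% |
| 90% Wald | 26.0% |
| 90% Wilson or Agresti-Coull | 23.1% |
| 90% mid-P | 24.9% |
| 90% Jeffreys | 23.8% |
| 90% Sterne | 25.1% |
| 90% Blaker | 26.1% |

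Keeping the 90% Clopper-Pearson interval, a maximum near 23.5% needs about 14 patients (23.6%; 15 patients give 22.8%).

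*How often would the stated bound be exceeded?* It is exceeded whenever 3 to 7 patients respond. The plan gives no target rate for MTOR. If the 30% targeted for TSC1/TSC2 is borrowed as an assumption, that happens with probability 62%; at 40% it is 82%.

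**Tumour-site probability.** P(at least 1 of 10) = 1 − (1 − 0.30)^10 = 1 − 0.0282 = 0.9718, which rounds to 0.97. The complement, 0 of 10, has probability 2.8%, against the 2% implied by 0.98. A value of 0.98 corresponds to 11 patients (1 − 0.7^11 = 0.9802), or to a response rate of about 32.4% with 10 patients.

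**Scope check.** The TSC1/TSC2 two-stage figures in 14.1 do reproduce: early stopping probability 0.848 (stated 85%), power 0.912 (stated 91%), type I error 0.066 (stated level 0.07). The problem is confined to the two figures above.

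**The case against.** The arithmetic is not in dispute; the case on the other side concerns weight. Nothing in the plan is derived from 23.5%. The MTOR signal rule is a count of responses and does not use the interval, 14.1 already warns that inference is limited, and the reported interval will be computed from the data and so will be right whatever the planning text says. The figure is also accurate at the threshold of 2 responses and conservative at 0 or 1.

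The 0.98 is a slip of 0.8 percentage points in a discretionary, exploratory rule for which no error rate is claimed. Expressing it as a relative increase in risk would mislead: a printed 0.98 may stand for a complement anywhere from 1.5% to 2.5%, so the relative excess of 2.8% could be about 13% or about 88%. Nor does the text suggest that 0.98 was a target to be preserved by looking at 11 patients instead.

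Most of this stands as a limit on importance. It does not rescue the sentence in 14.1. The text calls 23.5% a maximum, and the signal threshold is open-ended upward, so results of 3 to 7 responses are squarely among those the cohort is meant to detect. Where estimation is the main output of a small cohort, the one statement of its precision should be correct.

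**Conclusion.** The concern holds. The maximum 90% exact half-width for 10 patients is 27.8%, so 14.1 understates the worst case by 4.3 percentage points; 23.5% is the value at 2 or 8 responses only. The probability in 14.2 is 0.97, and the chance of 0 of 10 at a true 30% rate is 2.8% rather than about 2%. Both errors run in the favourable direction. The half-width carries the point; the 0.98 alone would be a minor correction and changes no decision.

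The result assumes that the exact interval is the usual equal-tailed Clopper-Pearson one and that the cohort reaches 10 patients. With 9 patients the maximum would be 29.0%. The primary TSC1/TSC2 design is unaffected.

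**What to change.** In Section 14.1, state that the maximum half-width of the 90% exact interval for 10 patients is 27.8%, reached at 5 responses, and that it is 23.5% if 2 responses are seen. In Section 14.2, replace 0.98 with 0.97; giving the 2.8% chance of 0 of 10 beside it would make the basis of the site rule plain. If the sponsor did intend a 0.98 probability, the look would have to come at 11 patients, but correcting the printed figure is enough.

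The cost is two numbers in the text, both slightly less favourable. Sample size, the response threshold and the conduct of the trial stay as they are.
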